## Missing Data

In the event of missing data, we will contact participants immediately. If a participant drops out, we will attempt to gather follow-up information. However, if they refuse to be contacted or otherwise lose contact with the investigators, we will censor data at point of loss. Two statistical approaches will be used to handle missing data. First, we will use inverse probability weighting with propensity scores. This is a two-step procedure in which we first model the probability of missingness as a function of baseline covariates and previous outcomes. Next, the inverse of the resulting predicted probabilities (from the logistic regression model) serve as weights in our proposed model of the response (e.g., salivary cotinine at follow-up). We will compare these results to a more conservative intent to treat approach as a final step.

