## E. Statistical Methods

### Power Analysis

Complete substitution between LWD vs. HWD products is the primary outcome of the study, as rate of product substitution will likely drive the outcomes for all of the other aims; thus, we will estimate power for the proposed study based on this outcome at the 3-month follow-up. There are no direct data available on which we can base sample size estimates for the proposed study. The closest estimate for the LWD arm was based on the 3-month, 7-day point prevalence abstinence rate for the nicotine EC (21.5%); however, as smokers in this study were motivated to quit smoking, set a quit date, and were provided cessation counseling, we conservatively estimate that the percent of complete substitution will be lower in the LWD group (15%). For the HWD group, we will assume a substitution rate of 30% based on the 2-month abstinence rate for HWD products found in the only prospective trial of HWD use. As such, a total of 453 patients (151/group) will be enrolled into the study. This sample size will provide about 80% power to detect a 15% difference in complete substitution between LWD and HWD groups for a two-sided .05 level chi-squared test. In the sample size calculation, we assume the complete substitution rates are 15% and 30% for the LWD and HWD groups. Our estimates of sample size adjust for attrition rates of 20% in each arm. These attrition rates are a conservative estimate based on [name] previous research. We are confident that with a total sample size of 453 participants (n=363 after accounting for attrition), we will have adequate power to test our primary aim. It is important to note that this sample size is deliberately conservative, as it does not assume the availability of repeated outcome measures that will be taken throughout the study. By choosing models that utilize longitudinal data, we will be increasing the power to detect differences between arms.

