## Examination of First and Second Generation E-cigarettes

**Aim 1:** The focus of aim 1 is the examination of differential levels of (Hyp 1a) substitution between LWD and HWD, and (Hyp 1b) number of cigarettes smoked and nicotine dependence between G1, G2 and control. *Hypothesis 1a:* Complete substitution rates, at the end of the Product Trial Phase (3 months) and at both Surveillance Phase Visits (6 and 12 months), will be compared between LWD and HWD arms using multiple logistic regression models. If necessary, models will adjust for baseline variables such as age, gender, number of cigarettes per day and/or randomization stratification factors. The GEE model will be performed for the repeated measure analysis of complete substitution rate across multiple visits.

*Hypothesis 1b:* If needed, we will apply a normalizing transformation to the response measure (e.g., taking the logarithm of cigarettes per day) before proceeding with the analysis, as a means of removing the effects of potential outliers. A single linear mixed effects regression model will be used to simultaneously estimate the product arm effects on outcomes (i.e., cigarettes per day, nicotine dependence, motivation to quit smoking/nicotine) at 1, 3, 6 and 12-month follow-ups, with a subject-specific intercept included to account for within-subject correlation in the outcome over time. We will control for baseline value of the outcome and potential confounders (including any variables not equally distributed between groups). Product arm will be coded using two dummy variables to account for the three product arms. Modeling is done using a likelihood-based approach and thus makes use of all available data (on the ITT sample) to produce consistent estimates of the regression parameters.

**Aim 2:** The focus of aim 2 is the examination of changes over time in biomarkers of toxicant exposure (Hyp 2a) between LWD, HWD and UBC, and (Hyp 2b) among LWD vs. HWD users who completely switch.

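### The missing-data weights are inverted: the plan weights by 1/P(missing) instead of 1/P(observed), which adds dropout bias rather than removing it

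*Combined protocol and SAP*

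**What the plan says.** The Missing Data section (E. Statistical Methods) promises two approaches. The first is named plainly: "First, we will use inverse probability weighting with propensity scores". In step one, "we first model the probability of missingness as a function of baseline covariates and previous outcomes". In step two, "the inverse of the resulting predicted probabilities (from the logistic regression model) serve as weights in our proposed model of the response". The only example given of a response is salivary cotinine, and nothing limits the method to particular outcomes. The second approach is a comparison: "We will compare these results to a more conservative intent to treat approach as a final step". No rule for missing values is given for it. For participants who cannot be followed, "we will censor data at point of loss".

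Three other places bear on the point:

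- Power Analysis names complete substitution, LWD versus HWD, as the primary outcome and says "Our estimates of sample size adjust for attrition rates of 20% in each arm".
- Data Analytic Plan, Hypothesis 1a, analyses that outcome by logistic regression at 3, 6 and 12 months and by GEE across visits. Adjustment for baseline variables or stratification factors is optional.
- Data Analytic Plan, Hypothesis 1b, uses a mixed model, which Aims 2 and 3 reuse: "Modeling is done using a likelihood-based approach and thus makes use of all available data (on the ITT sample".

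**The concern.** The event modelled in step one is missingness, and step two inverts the prediction from that same model. The weight is therefore 1/P(missing). No section takes the complement or mentions the probability of being observed.

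Inverse probability weighting works by letting each completer stand in for similar people who were lost, so completers with a high chance of dropout must count most. Under the stated rule they count least, and those almost certain to stay count most. Very small predicted probabilities of missingness also produce very large weights.

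The primary outcome is the most exposed. Unweighted GEE is not generally valid when dropout depends on earlier outcomes, which is the dependence that step one models, so correct weights matter there. Complete substitution also needs an exhaled CO reading (Outcome Measures). A questionnaire emailed after a missed visit cannot supply one, so full verification depends on attendance.

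**Working it through.** **The plan's own figure.** Inputs from Power Analysis: 15% versus 30%, two-sided 0.05, 80% power, 20% attrition. The pooled-variance formula gives

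n = [1.96·√(2·0.225·0.775) + 0.8416·√(0.15·0.85 + 0.30·0.70)]² / 0.15² = 120.5, so 121 per arm.

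Then 121/0.8 = 151.25, against the stated 151; 3 × 121 = 363, as stated. Power at 121 per arm is 80.2%. The sample size reproduces and is not in dispute; it only fixes the rates and attrition used below.

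**Why the inversion matters.** Let p(x) be the probability of missingness at covariate value x, and f(x) the covariate distribution of everyone randomised. Observed participants are distributed in proportion to (1 − p)f.

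- Weight 1/(1 − p): (1 − p)f/(1 − p) = f. The full population is restored.
- Weight 1/p: (1 − p)f/p. The distribution moves further from f, in the direction dropout had already pushed it.

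| P(missing) | As written, 1/p | Correct, 1/(1 − p) |
|---|---|---|
| 5% | 20.0 | 1.05 |
| 10% | 10.0 | 1.11 |
| 30% | 3.33 | 1.43 |
| 35% | 2.86 | 1.54 |

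**Illustration.** Assumptions not in the documents: two equal strata of a baseline covariate such as dependence; 20% average dropout, split unequally and in the same way in both arms; dropout random within stratum; substitution 40%/20% by stratum in HWD and 20%/10% in LWD, which average to the plan's 30% and 15%.

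Estimate = Σ(1 − p)·w·s / Σ(1 − p)·w, where s is the stratum's substitution rate. For HWD with a 10/30 split:

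- Correct: (0.40 + 0.20)/2 = 30.0%.
- Unweighted: (0.9·0.40 + 0.7·0.20)/1.6 = 31.25%.
- As written: (9·0.40 + 2.333·0.20)/11.333 = 35.9%.

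The bias in the HWD rate is +5.9 points as written, against +1.25 unweighted.

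| Dropout split | Unweighted: HWD, LWD, difference | As written: HWD, LWD, difference | 1/P(observed) | Effective n, as written |
|---|---|---|---|---|
| 15/25 | 30.6, 15.3, 15.3 | 33.1, 16.5, 16.5 | 30.0, 15.0, 15.0 | 94% |
| 10/30 | 31.3, 15.6, 15.6 | 35.9, 17.9, 17.9 | 30.0, 15.0, 15.0 | 82% |
| 5/35 | 31.9, 15.9, 15.9 | 38.2, 19.1, 19.1 | 30.0, 15.0, 15.0 | 71% |

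Effective n is (Σw)²/Σw² as a share of those observed. For 10/30: 11.333²/(0.9·100 + 0.7·11.11) = 1.314, and 1.314/1.6 = 82%. Correct weights give 2²/2.540 = 1.575, or 98%.

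**A steeper gradient, and dropout that differs by arm.** Now take substitution of 45%/15% (HWD) and 22.5%/7.5% (LWD), which have the same averages, with weights computed within arm. Ranges run over the same three splits.

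| Scenario | Truth | Unweighted | As written | 1/P(observed) |
|---|---|---|---|---|
| Same dropout pattern in both arms | 15.0 | 15.5 to 16.4 | 17.3 to 21.2 | 15.0 |
| Covariate-dependent dropout in HWD only (LWD 20/20) | 15.0 | 15.9 to 17.8 | 19.6 to 27.3 | 15.0 |
| No true difference (22.5%/7.5% in both arms), dropout pattern in one arm only | 0 | 0.5 to 1.4 | 2.3 to 6.2 | 0 |

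**The case against.** The best case for the plan is that this is a slip in wording. The method is named correctly, the section gives no formula or event coding, and modelling missingness can loosely mean fitting a logistic model to the missing/observed indicator. An analyst who knows the method might invert the right probability. That is possible, but the plan as written fixes the wrong one, and silently correcting it would be an undocumented departure from the plan.

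Several limits on the harm stand:

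- Bias needs a predictor shared by dropout and outcome. Without one, the wrong weights only cost precision.
- Nicotine dependence is a stratification factor, and Hypothesis 1a allows adjustment for such factors. A response model that conditions correctly on every shared predictor mainly loses precision. But adjustment is optional, and the adjusters named are baseline variables, whereas step one also uses previous outcomes.
- The shift is smaller on the odds-ratio scale that logistic regression reports. In the 10/30 example the odds ratio is 2.43 in truth, 2.45 unweighted and 2.56 as written, about 5% too high. The risk ratio stays at 2.0 in that example. With the same mechanism in both arms and no true effect, no false difference arises.
- The mixed models for Hypothesis 1b and Aims 2 and 3 need no weights when dropout depends only on observed data, so unweighted fits are unaffected.

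The intent-to-treat comparison is not a safeguard, because its handling of missing values is undefined.

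**Conclusion.** The concern holds. The stated weight, 1/P(missing), is invalid, and no other section repairs it. Under the first set of assumptions the true 15.0-point difference is reported as 16.5 to 19.1 points, against 15.3 to 15.9 with no weighting at all. Effective sample size falls to between 94% and 71% of those observed. With a steeper gradient and dropout that differs by arm, a spurious difference of 2.3 to 6.2 points can appear where none exists.

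These sizes rest on assumed strata and dropout patterns; only the 15%, 30% and 20% come from the plan. The inversion itself rests on no assumption. Sample size and power are untouched. Because the rule is the first-listed missing-data method and reaches the primary outcome, it must be corrected before analysis.

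**What to change.** Replace the two-step description with the following: at each visit, model the probability that the outcome is observed, given arm, baseline covariates and previous outcomes. Weight each observed record by the inverse of that probability, cumulated over visits and stabilised. State that these weights apply to the week-12 logistic model and to the GEE for complete substitution.

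The essential correction is 1/P(observed); cumulating and stabilising are good practice for repeated visits. In the same edit, define how the intent-to-treat comparison treats missing outcomes, so that it can serve as a check.

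The cost is one or two sentences for the weights and one for the comparison. There is no change to data collection, sample size or participant burden.

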## Examination of First and Second Generation E-cigarettes

## **F. Gender/Minority/Pediatric Inclusion for Research**

### **Inclusion of Women and Minorities**

According to 2018 US Census estimates, 51.3% of Columbus residents are female. We expect that the proportion of female participants will likely be somewhat larger given our previous studies with smokers (55-62% female). According to 2018 US Census estimates, the racial composition of individuals living in Columbus is 60.5% White, 28.3% Black or African American, 5.2% Asian, 0.2% American Indian/Alaska Native, 0.0% Native Hawaiian/Other Pacific Islander, and 4.1% two or more races. The ethnic composition of individuals living in Columbus is 6.0% Hispanic/Latino and 94.0% Non-Hispanic/Latino. We expect that our distribution will be similar to these but may potentially have a larger distribution of ethnic and racial minorities, given our previous studies and that menthol smokers tend to more often be black or Hispanic. However, we will continuously monitor enrollment in order to ensure that we are meeting recruitment goals to avoid under-recruiting minorities. If the targeted enrollment for minorities is not met because they do not respond to the advertisements, we will make special efforts to solicit their participation by advertising in community newspapers, local church organizations, and community centers.

### **Inclusion of Children**

Participation in the proposed study will be restricted to individuals 21 years of age and older. This exclusion is for two primary reasons: 1) the use of tobacco products by minors is illegal, and 2) the concern of introducing and potentially addicting children and adolescents to another tobacco product.

## **G. Human Participants**

### **Potential Risks**

The research protocol calls for current smokers who do not plan to quit smoking within the next three months to attempt to completely substitute a LWD e-cigarette, a HWD e-cigarette, or to continue to smoke their usual brand of cigarette as they wish. Participants will not be provided any more instructions for use, and non-use of e-cigarettes is a permissible outcome. E-cigarettes are no more harmful than conventional cigarettes, and there is some evidence that they may offer reduced harm. Questionnaires, exhaled breath and urine collection procedures are all non-invasive and involve minimal risk to study participants. Potential risks are as follows: a) risk of using e-cigarettes, b) dual use of cigarettes and e-cigarettes, c) loss of confidentiality or privacy, d) potential for undermining smoking cessation, e) lack of appropriate storage of nicotine-containing products in a house with children and pets, f) slight risk of discomfort, bruising and infection with blood draw, and g) slight risk of discomfort and very low risk of infection with oral (buccal) cell collection.

The Centers for Disease Control and Prevention (CDC), the Food and Drug Administration (FDA) and several states, and federal health departments are investigating a multi-state outbreak of severe lung disease associated with using e-cigarette/vaping products. The investigation is ongoing and has not identified a cause, but all cases have reported use of vaping devices. The majority of patients have reported vaping cannabis oil,

### Examination of First and Second Generation E-cigarettes

such as THC, obtained on the black market or other sources. In addition, one of the chemicals that has been possibly linked is Vitamin E acetate (tocopheryl acetate) added to e-liquid cartridges and pods.

The FDA has advised consumers to protect themselves by not using vaping products of any kind obtained off the street or black market and to refrain from using THC oil or modifying/adding any substance to vaping products purchased at stores. We will recommend that participants use only the products that we provide them for this study and do not add any substances to the e-liquids or alter the device in anyway.

### Recruitment and Informed Consent

At first contact, all participants which include women and minorities will be screened according to the studies inclusion/exclusion criteria. Those who are eligible will be given a brief verbal overview of the study and invited to participate. Informed consent (including a description of the nature, purpose, risks, and benefits of the study) will take place through both oral and written explanation of the study. The voluntary nature of the study and the participant's right to withdraw at any time will be stressed during the consent process; a copy of the informed consent will be provided to the participant in written form at the time of consent for them to keep. Informed consent will be collected by IRB-approved study personnel.

Recruitment scripts and materials, consent forms, and all study procedures will be approved by the OSU Institutional Review Board. All participants will provide written consent before any study data are collected.

### Protections Against Risk

Efforts to reduce risk are as follows:

1. Risk of using e-cigarettes: The risk of side effects and adverse events are very low. These products are sold online, and at e-cigarette specialty stores and convenience stores nationwide, without a prescription. Nevertheless, all participants will be screened for general medical precautions (pregnancy, cardiovascular disease) and monitored for adverse events during the study period. Study personnel will assess for adverse events via self-report at all follow-up visits. Smokers will also be provided a study phone line to report an adverse event between follow-up visits. Any serious adverse events will be reported to the PI and then to the OSU IRB and potentially to the NIH. We will withdraw participants who have a serious adverse event, or become pregnant or begin to breastfeed. The most likely adverse (potential for nicotine overdose) event is anticipated to be rare (<5% in [name] previous studies) and mild (nausea, headache, disrupted sleep) event will be handled quickly (i.e., advice to participant to reduce or stop EC use). [name], a physician, will also be available for medical oversight and to handle any questions regarding reported adverse events. Lab studies of toxin exposure suggest that ECs incur no greater risk to health than do conventional cigarettes. Indeed, e-cigarettes generally show lower levels of harmful and potentially harmful constituents. To date, five e-cigarette studies discuss adverse events (3 survey and 2 randomized clinical trials), reporting mild and tolerable side effects that generally resolved completely over time with continued use (90% of cases); the most predominant of which were mouth/throat irritation, cough, and headache. In both randomized clinical trials, no serious adverse events were reported and the e-cigarette group and the nicotine patch group had comparable levels of adverse events. The most common were mouth irritation, throat irritation, dry cough and headache.

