Participants who meet the following eligibility criteria will be contacted by phone and asked to attend the first baseline visit. Inclusion criteria: 1) smoke  $\geq 5$  cigarettes per day for the past year; 2) not currently engaged in a quit attempt ; 3) read, write, and speak in English; 4) report at least minimal interest in switching to an alternative product ( $>$  "not at all" on a Likert scale); 5) have not regularly used a tank system, mechanical mod, or advanced personal vaporizer EC, though previous use of cig-a-like devices of 10 or less days in the last month will be allowed; 6) plan to live in the local area for next year; 7) have access to a smart phone; 8) have access to email and 9) be 21 years of age or older. Exclusion Criteria: 1)  $< 21$  years old 2) unstable or significant medical condition such as respiratory, kidney, or liver disease that could potentially affect biomarker data; 3) unstable or significant psychiatric conditions (past and stable conditions will be allowed); 4) history of cardiac event or distress within the past 3 months; 5) currently pregnant, planning to become pregnant, or breastfeeding (pregnancy and breastfeeding status will continue to be evaluated throughout the study at each visit); and 6) do not reside in the same household as a participant currently active (have not completed all study visits) in the study. If a participant is ineligible for the study at the time of screening, the participant can be reassessed at a later time to determine if they are now eligible i.e. A participant meets all other eligibility criteria, but is not eligible because they are currently pregnant or breastfeeding. The participant can submit a new screener after they are no longer pregnant or breastfeeding and can be reassessed for eligibility. Reassessment for eligibility will vary based on previous ineligibility criteria and will be determined on a participant by participant basis.

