**Surveillance Phase:** The purpose of this 40-week period is to assess how LWD vs. HWD use evolves over time; specifically, continued use of product assigned, transitions to other types of EC products, smoking behavior and patterns, as well as continued monitoring of biomarkers of toxicant exposure and effect over the long-term. During this phase, follow-up study visits will occur at +26 and +52 weeks, and will continue to include computerized questionnaires as well as collection of biomarkers. However, use of the daily online diary will be reduced to only the week prior the 26- and 52-week visits. Participants will be given atomizers throughout the enrollment period but will not be provided ECs, e-liquid or conventional cigarettes during this phase. Use of both will continue to be tracked. Those continuing to use any tobacco or EC product at the end of the surveillance phase will be strongly advised to quit smoking/vaping and provided the number to the Ohio Tobacco Helpline and other local smoking cessation resources.

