### Examination of First and Second Generation E-cigarettes

however, alternative methods may be employed if issues arise with the preferred method (e.g., participant has run out of minutes; cellular providers are not compatible). If participants are unable to complete a daily diary using the link to the online survey, they may be contacted by other methods by Switch study staff to complete the daily diary. If participants become ineligible during the course of the study, compensation for daily diaries will be given only for diaries completed up to the date that they were deemed ineligible. Diary data will provide several outcome variables: 1) Smoking behavior: conventional cigarettes smoked per day and 2) EC use: amount of e-liquid use and frequency of EC use; and 3) EC flavor: report EC flavors used that day (categories for flavors along with examples will be provided).

Table 3. Outcome Measures		Baseline		Randomized Product Trial			Surveillance		
Weeks		-1	0	1	4	8	12	26	52
Self-Report Measures									
Sampling Procedures			X	X	X	X			
Product/Tobacco Use History and Exposure	X								
Demographic History	X								
Daily online e-cigarette and smoking diary	X	X	X	X	X	X	X		X
Timeline Follow-Back	X	X	X	X	X	X	X		X
Cigarette Dependence Scale 2			X	X	X	X	X		X
Cigarette Dependence Scale	X	X	X	X	X	X	X		X
Product Evaluation Scale			X	X	X	X			
Cigarette Evaluation Scale		X		X		X	X		X
Drug Effects/Liking Questionnaire (cigarettes and e-cigarettes)		X		X		X	X		X
Cigarette Purchase Task (cigarettes and e-cigarettes)			X	X	X	X			
E-cigarette product transitions questionnaire			X	X	X	X	X		X
Motivation Rulers (cigarettes and nicotine)	X	X	X	X	X	X	X		X
Biomarker Measures									
Total NNAL (urine)			X		X		X	X	X
Total NNN (urine)		X		X		X	X		X
N  -HOMe-dAdo (blood)		X		X		X	X		X
N  -ethylidene-dGuo (blood)		X		X		X	X		X
Total Nicotine Equivalents (urine)		X		X		X	X		X
Creatinine (urine)		X		X		X	X		X
q-PADDA (oral cells)		X		X		X	X		X
Exhaled breath CO	X	X	X	X	X	X	X		X
Pulmonary Function		X		X		X	X		X
Pregnancy Test	X	X	X	X	X	X	X		X
Saliva Sample		X		X		X	X		X

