*Hypothesis 2a:* The biomarker outcome measures analyzed will include mean levels of specific biomarkers at all follow-up time points. The analysis of biomarkers of toxicant exposure will be analyzed similar to outcome variables in Hypothesis 1b. Again mixed effects models will be used for analysis and resulting contrast estimates comparing group effects over time will be used as measure of effect. We will again apply a normalization transformation but will also include potential confounding factors measured in the

*Biomarker Modifier Questionnaire* in the model. *Hypothesis 2b:* Similar analyses to Hypothesis 2a will be performed but only among the subset of LWD and HWD users who completely switch.

**Aim 3:** The focus of Aim 3 is the examination of changes over time in biomarkers of toxicant effect (Hyp 3a) between LWD, HWD and UBC, and (Hyp 3b) amongst LWD vs. HWD users who completely switch. For Aim 3 (Hypothesis 3a and IRB NUMBER: 6379 3b), we will run the same analyses as in Aim 2, but the biomarker outcome measures analyzed will include mean levels of DNA damage and pulmonary functioning at all follow-ups.

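### Withdrawal for a serious adverse event, pregnancy or breastfeeding should stop product but keep outcome follow-up: a minor change with a small expected effect

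*Combined protocol and SAP*

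**What the plan says.** The rule is in section G, Protections Against Risk, item 1: "We will withdraw participants who have a serious adverse event, or become pregnant or begin to breastfeed". It appears under the risk of using e-cigarettes, but it speaks of participants in general and sets no condition on arm, phase or whether the event is related to product.

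The checks that trigger it run to week 52 in all arms. Under Participants, "pregnancy and breastfeeding status will continue to be evaluated throughout the study at each visit". Adverse events are assessed at every follow-up visit, and all participants have visits to week 52. After week 12 there is little product to stop: "Participants will be given atomizers throughout the enrollment period but will not be provided ECs, e-liquid or conventional cigarettes during this phase".

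Two places bear on what happens to the data afterwards:

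- The daily-diary text under Outcome Measures says of participants who become ineligible that "compensation for daily diaries will be given only for diaries completed up to the date that they were deemed ineligible".
- Section E, Missing Data, says "If a participant drops out, we will attempt to gather follow-up information", and censors at the point of loss if the person refuses contact or cannot be reached. It then plans inverse probability weighting, which will "model the probability of missingness as a function of baseline covariates and previous outcomes".

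For Aim 3, "the biomarker outcome measures analyzed will include mean levels of DNA damage and pulmonary functioning at all follow-ups".

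**The concern.** A safety rule needs to end exposure. It does not need to end measurement. If withdrawal here means leaving the study, follow-up stops because of an event after randomisation that can itself alter the outcome. A serious respiratory illness changes spirometry, and a pregnancy can change smoking and biomarkers.

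The weights and the likelihood-based mixed model would represent these people only if, given baseline and previous outcomes, the event carried no further information about later outcomes. That is doubtful, and the data could not test it, because nobody with the event would remain under observation to stand in for the others.

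What is at stake is weeks 26 and 52, mainly lung function and biomarkers. A participant with a serious lung event would be reported to the IRB but might have no later spirometry. For usual-brand controls, and for everyone after week 12, withdrawal would remove data while taking away no study-supplied e-cigarette, and after week 12 no supplied cigarettes either.

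**Working it through.** **1. Does collection stop?** The texts side by side:

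- Item 1 handles mild events by advising the participant to reduce or stop e-cigarette use, and handles serious ones by withdrawal. So withdrawal reads as more than stopping product.
- The diary text ends payment at ineligibility. It is silent on visits and specimens.
- Missing Data covers someone who drops out. It does not mention people whom staff withdraw, and it promises an attempt at unspecified information, not the scheduled visits.
- Questionnaires may be emailed to those who cannot attend, but that cannot supply exhaled CO (part of the definition of complete substitution), specimens or spirometry.

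Stopping is therefore the more likely reading, but it is an inference. The consent pages, which might settle it, are not in the copy reviewed.

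**2. The plan's own sample size (section E, Power Analysis).** Inputs: 15% vs 30%, two-sided 0.05, 80% power, 20% attrition.

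n = [1.960·√(2·0.225·0.775) + 0.842·√(0.15·0.85 + 0.30·0.70)]² / 0.15² = 120.5, so 121 per arm. Then 121/0.8 = 151.25, against the stated 151. Power at 121 per arm is 80.2%. The design reproduces.

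**3. How many people?** The documents give no rate for serious adverse events or pregnancy. They report no serious adverse events in two earlier randomised trials or in 20 caregivers, although 0 of 20 still allows up to 1 − 0.05^(1/20) = 13.9% (one-sided 95% limit). Assumption: 1-5% per arm over 52 weeks, evenly spread.

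| Rate r | Per arm, 151·r | By week 12 (×12/52) | Later (×40/52) |
|---|---|---|---|
| 1% | 1.5 | 0.35 | 1.16 |
| 2% | 3.0 | 0.70 | 2.32 |
| 5% | 7.6 | 1.74 | 5.81 |

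**4. Complete substitution.** Let q be the proportion withdrawn in each arm, with 30% vs 15% among those kept. The difference is 15(1 − q) points if the withdrawn behave alike in both arms. The extreme bounds are 15(1 − q) ± 100q, reached only if all the withdrawn substitute in one arm and none in the other.

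| Time | q | If alike | Extreme bounds |
|---|---|---|---|
| Week 12 | 0.23% | 14.97 | 14.73-15.20 |
| Week 12 | 1.15% | 14.83 | 13.67-15.98 |
| Week 52 | 1% | 14.85 | 13.85-15.85 |
| Week 52 | 2% | 14.70 | 12.70-16.70 |
| Week 52 | 5% | 14.25 | 9.25-19.25 |

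The week-52 rows borrow the planned week-12 rates. Week-12 power is 79.5% if 2 per arm are lost beyond the 20% allowance (119 per arm).

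**5. Lung function at week 52.** If the event lowers the outcome by d SD and those people vanish, the arm difference is off by roughly (q₁ − q₂)·d. A simulation gave similar values. It used 2,500 trials, 151 per arm, about 19% other dropout depending on the previous outcome, a correlation of 0.7, and weights from arm, baseline and previous outcome. It compared the planned weighting with the same weighting when follow-up continues.

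| Event rates | Drop | (q₁ − q₂)·d | Simulated bias (SD) |
|---|---|---|---|
| 2% or 5% in both arms | none | 0 | 0.000 |
| 2% / 5% in both arms | 1 SD | 0 | 0.000 / 0.001 |
| 2% vs 1% | 1 SD | 0.01 | 0.009 |
| 5% vs 1% | 1 SD | 0.04 | 0.036 |
| 5% vs 1% | 2 SD | 0.08 | 0.077 |

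The SD of the estimate was 0.11-0.12. As a rough check, √(2/121) = 0.13 without baseline adjustment.

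**6. Extra visits if follow-up continues.** With events evenly spread, expected visits remaining are (1 + 4 + 8 + 12 + 26 + 52)/52 = 1.98 per person.

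- Of the 233 still to be recruited: 233·0.01·1.98 = 4.6, to 233·0.05·1.98 = 23.1.
- Of all 453: 9.0 to 44.9.

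**The case against.** The best defence is that withdrawal is undefined and sits in a list of protections against product risk, so it could mean stopping product only. Missing Data censors only those who refuse contact or are lost. A participant withdrawn for pregnancy is neither, so the promised follow-up could fairly be read to include her. The diary sentence concerns payment alone. This stands in part: the documents do not state that outcomes are discarded, and a reader who infers that goes further than the text. What remains is that no sentence keeps these people in the scheduled visits, and the nearest ones lean the other way.

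A reader might also infer that the ITT label is wrong. The Hypothesis 1b model "makes use of all available data (on the ITT sample) to produce consistent estimates of the regression parameters". That criticism does not hold: missing later visits does not remove anyone from the randomised set, and earlier data stay in.

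A third objection is that bias needs event rates or consequences to differ by arm, and the documents show no such difference. This stands. Section G (Potential Risks) describes an outbreak of severe lung disease in which all cases reported vaping, so a difference is conceivable. The same text says that most of those patients had vaped cannabis oil, and it gives no rate for study products.

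Finally, the fix cannot supply spirometry or blood that would be unsafe to take, and it comes after 220 participants were already recruited. Both points stand and limit the gain.

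**Conclusion.** The point holds as a minor one. As written, the rule probably ends outcome collection after a serious adverse event, pregnancy or breastfeeding in every arm to week 52. The loss would be related to the outcome, beyond repair by the planned weights, and irrecoverable.

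Its expected size is small. The effect on the week-12 primary endpoint is negligible, and a reader should not infer a threat to the primary comparison or to power. The wide week-52 bounds for substitution need both the 5% rate and opposite behaviour by all the withdrawn in the two arms. For lung function the simulated bias stays below one standard error even at 5% vs 1% with a 2 SD drop, and is essentially nil when rates and consequences are equal. No bias has been demonstrated.

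These sizes rest on an assumed 1-5% event rate spread evenly over the year, and on the simulation's assumed dropout and correlation. The case for acting is that the change is cheap and cannot be made once the data are lost.

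**What to change.** Replace the sentence in Protections Against Risk, item 1, with: *After a serious adverse event, pregnancy or start of breastfeeding, study product stops (where supplied) and the participant is asked to continue the remaining outcome visits, omitting any unsafe procedure.* In addition:

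- State in Missing Data that the follow-up of dropouts also applies to participants whom the study withdraws.
- Change the diary text so that diaries completed afterwards are paid.
- Analyse these participants in their randomised arm, and report the number and reasons by arm.

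**Cost.** One IRB amendment with consent text. At 1-5%, about 5-23 extra already-scheduled visits among the 233 still to be recruited, plus any for earlier enrollees still in follow-up, and at most 9-45 across all 453.

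Under Retention, a specimen visit pays $5 + $20 + $20 = $45, or $52 with parking. Only five visits are specimen visits ($100 at $20 each), so these are ceilings: 4.6 × $45 to 23.1 × $52, or about $210-1,200 for the 233, and about $400-2,300 for all 453. Diaries at $1 each add about 42·12/52 + 7·26/52 + 7 = 20 entries per person, roughly $90-460 across all 453. Assay costs are extra and are not given.

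**Limits.** Some spirometry or blood data will still be missing, and outcomes already lost cannot be recovered.
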